### 7.2 Safety set

The Safety set will comprise all patients who received at least one dose of IMP. Patients will be grouped according to the actual treatment received. Patients randomized to placebo that incorrectly received one dose of anakinra or more will be included in the corresponding anakinra group. Patients randomized to anakinra who incorrectly received only placebo will be included in the placebo group.

The Safety set will be used for the safety analyses.

# 7.3 Pharmacokinetic (PK) set

The PK set will comprise patients who received anakinra without any major protocol deviations as judged by the Clinical Pharmacology Scientist before DBL with respect to administration of IMP. All patients with at least one PK measurement will be included in the analysis set for the analysis of anakinra plasma concentrations. Patients with repeated dose PK should not have any major protocol deviations with respect to the repeated dose PK measurements.

The PK set will be used for evaluating the PK of anakinra.

#### 7.4 Protocol deviations

Protocol deviations related to study inclusion or exclusion criteria, conduct of the study, patient management or patient assessment will be reviewed prior to DBL and described in the CSR as appropriate.

Major protocol deviations that will lead to exclusion from the mITT analysis set are the following:

- Patient failed to satisfy major disease-specific entry criteria in accordance with the adapted ILAR or Yamaguchi criteria, as detailed in the CSP.
- Patient did not get any dose of IMP.

# 8 General issues for statistical analysis

The comparison of interest is between anakinra (2 mg/kg and 4 mg/kg combined) and placebo. Due to the small number of patients in the individual dose groups of anakinra, summary tables (except for the drug exposure summary) will not provide results by individual dose groups. Likewise, the randomization was stratified by age at onset of disease (< 16 years,  $\geq$  16 years) and glucocorticoid use (yes, no), but due to the very small number of patients for levels of the stratification factors within each treatment group, descriptive statistics and statistical analyses will generally not be performed by stratification factors. For primary and key secondary efficacy endpoints, dose-level information and stratification allocation will be included in a patient listing.

All statistical tests will be two-sided and performed using a 5 % significance level, if not stated otherwise. Results will be presented as the estimated value for each treatment group, anakinra and placebo, the estimated difference between groups, the associated 95 % two-sided confidence interval and p-value. P-values from statistical analyses will be presented to three decimal places with values below 0.001 displayed as <0.001 and 95 % confidence intervals will be presented to one more decimal place than the raw data.

Continuous data will be summarized using descriptive statistics: n, mean, SD, median, minimum and maximum, unless otherwise indicated. Minimum and maximum will be presented to the same number of decimal places as the raw data and mean, SD, and median will be presented to one more decimal place than the raw data.

Categorical data will be summarized using counts and percentages. Percentages will be suppressed when the count is zero, however the category will still be displayed. The denominator for all percentages will be the number of patients within the treatment group for the population of interest, unless otherwise indicated. Percentages will be presented to one decimal place.

Statistical analyses will be performed using SAS software Version 9.4 (SAS Institute Inc, Cary, North Carolina, United States).

#### **8.1** Time windows

For the purpose of the statistical analysis and if not otherwise specified, all the variables (primary, secondary and exploratory variables) will be assigned to the visit/assessment timepoint in which they were collected depending on the following analysis time windows in Table 1.

Table 1 Time windows

Visit	Week	Study Day	Study Day window
1	Baseline	1	≤1
2	1	8	2-11
3	2	15	12-22
4	4	29	23-43
5	8	57	44-71
6	12	85	≥ 72

Unscheduled visit data will be considered when assigning assessments to the analysis visit. If more than one assessment of the variable (scheduled or unscheduled) falls in the same time window but on different days, the closest to the scheduled visit day will be taken, or the earlier, in the event the values are equidistant from the nominal visit date. If several measurements are collected during the selected day, the average (for numeric values)/worst (for categorical values) of the measurements will be taken.

In summaries of extreme values as opposed to visit-based summaries, all post baseline values collected are used including those collected at unscheduled visits regardless if the value is closest to the scheduled visit date or not. For summaries at a patient level, all values should be included, regardless of whether they appear in a corresponding visit-based summary, when deriving a patient level statistic such as a maximum.

Listings will display all values contributing to a time point for a patient.

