There is limited information about the PK of anakinra in SJIA patients, and no information about the PK of anakinra in AOSD patients. The PK of anakinra is however well characterized in healthy volunteers and RA patients. The bioavailability is high (~95%), t_{max} is about 6 hours and anakinra serum concentrations decline with a half-life of 4-6 hours following s.c. administration to RA patients. The exposure increases in approximate proportion to dose, accumulation is modest following once daily administration and approximately 80% of anakinra is eliminated by the kidney. In JIA patients trough anakinra concentrations were lower in the age group 3-6 years compared to older children and in 22 SJIA patients clearance was higher in children with a lower body-weight (28).

For a detailed description of anakinra characteristics, contraindications, warnings and precautions, adverse reactions and pharmaceutical properties, refer to the product information/monograph and the IB.

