Live vaccines is not allowed within 1 month prior to randomization and until after 1 month following the last study dose. Inactivated vaccines may be permitted according to the investigator's discretion. The investigator should instruct the patient to notify the study site about any new medications he/she takes after the start of the study drug. All medications and significant non-drug therapies administered after the patient starts treatment with study drug until Week 16_{TeI} must be listed on the concomitant medication CRF page.

Following the 12 week double blind treatment, the patient will be treated at the discretion of the investigator according to standard of care.

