6.5.5.6 Laboratory assessments

Clinically significant abnormal laboratory values should be reported as adverse events, except at baseline when they should be recorded as part of the medical history.

The laboratory lab manual will define which labs to prioritize to ensure that the maximum allowed blood volume is never exceeded in pediatric patients according to NIH guidelines or any local guidelines (54, 55). Blood sampling for the care of the patients should always have the priority over blood samples collected specifically for this study. For patients with a body

weight <15 kg, central laboratory hematology and coagulation samples should not be repeated at Week 1 visit, if not clinically indicated, in order to preserve blood volume.

All laboratory assessments should be performed also for patients <15 kg body weight at the Study Drug Discontinuation visit. If the Week 2 visit is performed after the Study Drug Discontinuation visit, central lab should also be collected at the Week 2 visit, if not exceeding the maximum allowed blood volume collection according to limitations in relation to the body-weight of the patient.

In case any of the safety central lab assessments cannot be analysed from the Week 12 visit the patient should be asked to return for an unscheduled visit to ensure that results are available for all lab assessments..

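### The open-ended Week 12 window lets a repeat CRP taken after the last dose stand as the Week 12 efficacy value when the Week 12 sample could not be analysed

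*SAP*

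**What the plan says.** SAP 8.1 decides which assessment represents each visit. Unless specified otherwise, "all the variables (primary, secondary and exploratory variables) will be assigned to the visit/assessment timepoint" in whose study-day window they fall. Table 1 gives Week 12 a nominal day of 85 and a window that opens on Day 72 and never closes. The section adds that "Unscheduled visit data will be considered when assigning assessments to the analysis visit". If values from different days share a window, "the closest to the scheduled visit day will be taken, or the earlier, in the event the values are equidistant". Nothing in the rule refers to the last dose or to the start of other treatment.

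Protocol 6.5.5.6 creates a late sample: "In case any of the safety central lab assessments cannot be analysed from the Week 12 visit the patient should be asked to return". That extra visit is outside the schedule, it exists to complete the set of laboratory results, and no deadline is set for it. Table 5 of the protocol places CRP, ferritin, hemoglobin and platelet count in the central panel.

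Protocol 6.5.1.7 puts the Week 12 visit about 24 hours after the last dose, or on the day of the last dose for patients in repeated-dose PK sampling, and remaining study drug is collected there. After that, under Protocol 6.4.6, "Following the 12 week double blind treatment, the patient will be treated at the discretion of the investigator according to standard of care".

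SAP 3.3.4 lists Week 12 ACR response, change in the four laboratory variables, JADAS27 and inactive disease among the other secondary efficacy endpoints. SAP 8.2.1 reports these on observed data.

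**The concern.** The objective behind these endpoints is efficacy during the 12 weeks of treatment. A repeat sample drawn days or weeks after dosing ended does not measure that. It reflects the patient off study drug, possibly on whatever the investigator started next. The SAP would still label it Week 12.

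CRP matters most because it feeds composites. A late CRP would be combined with joint counts, VAS scores and morning stiffness from the actual Week 12 visit, so one composite result would describe two different treatment states. The direction of the error is not predictable: CRP might rise after anakinra stops, or fall in a placebo patient who has begun other therapy. With about 12 patients, a single such value would be visible in the results.

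**Working it through.** The plan states no figure here to reproduce. The check applies its own assignment rule to possible visit dates.

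**Inputs**
- Window Day 72 onward, nominal Day 85, closest value taken, earlier one if tied (SAP 8.1).
- Scheduled Week 12 visit on Day 85 ± 2, that is Days 83 to 87 (Protocol Appendix 5).
- The only later scheduled contact is the Week 16 telephone call, at which no blood is drawn (Protocol 6.5.1.8).
- Half-life: "anakinra serum concentrations decline with a half-life of 4-6 hours following s.c. administration to RA patients" (Protocol 4.1).
- At least 12 patients expected, allocated 2:1 (SAP 4.2), taken here as 8 and 4.

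**Step 1. The parameter failed at Week 12.** The repeat is normally the only value in the window, so the closest-day rule has nothing to choose between. A repeat on Day 113, for example, would be the Week 12 value.

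**Step 2. The parameter was analysed at Week 12, but the repeat visit measured it again.** Compare distances from Day 85:

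| Week 12 visit | Distance | Repeat days that displace it |
|---|---|---|
| Day 83 | 2 | 84, 85, 86 (Day 87 ties, earlier kept) |
| Day 84 | 1 | 85 (Day 86 ties, earlier kept) |
| Day 85, 86 or 87 | 0, 1, 2 | none |

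A valid Week 12 value is therefore usually safe.

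**Step 3. Drug remaining.** Fraction = 0.5^(t / half-life), for half-lives of 4 h and 6 h:
- 24 h: 0.5^6 = 1.6% and 0.5^4 = 6.3%
- 48 h: 0.5^12 = 0.02% and 0.5^8 = 0.4%
- 72 h: 0.5^18 = 0.0004% and 0.5^12 = 0.02%

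**Step 4. Where the CRP goes.** SAP 12.4.2 plots individual CRP and JADAS27, shows ACR response in swimmer plots and counts inactive disease.
- JADAS27: CRP contributes up to (110 − 10)/10 = 10 of 57 points.
- ACR30: CRP is one of six components. It decides the result only if exactly two of the other five improved enough, or if at least three improved and one worsened by more than 30%. Even then, a second worsening must not already rule out response.
- Inactive disease: normal CRP is mandatory (SAP 8.5.4), so a late CRP could decide the result by itself when every other criterion is met.

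**Step 5. Largest effect of one patient on a percentage.** 1/8 = 12.5 points on anakinra; 1/4 = 25 points on placebo. This requires that CRP is the affected parameter and that its late value flips a binary result.

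**Step 6. Frequency.** Neither document gives a failure rate. Assuming 0 to 10% of patients and no dropouts, 0 to 0.10 × 12 = 1.2 patients would be affected.

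**The case against.** The strongest reply is that the route is narrow and little depends on it. Much of that stands.

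- Only the repeat laboratory visit normally reaches the open end of the window, and it normally matters only for a parameter that failed.
- A reader might infer that four efficacy variables are compromised. SAP 12.4.2 gives a Week 12 efficacy output to CRP alone among them. Hemoglobin, platelets and ferritin appear only in the laboratory summaries of SAP 13.3, where a repeat value serves the purpose of the protocol's instruction.
- A reader might infer that the late sample measures a CRP rebound. The documents give a serum half-life in RA patients, not a time course for CRP after stopping. The scheduled visit is itself 4 to 6 half-lives after the last dose, so residual drug alone does not separate a valid sample from an invalid one. What separates them is the further time without dosing and the possible start of standard of care, and the documents do support both.
- Inactive disease is arguable. The windows apply only where nothing else is specified, and SAP 8.5.4 ties the assessment to the Week 12 and discontinuation visits. It does not say that a later CRP is excluded, so the default window rule is the more natural reading.
- Listings will show the values contributing to each time point. That aids transparency, but the SAP does not require late values to be flagged.

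None of this stops the rule from assigning the late CRP to Week 12.

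**Conclusion.** The concern holds in a limited form. When a Week 12 central CRP cannot be analysed, the SAP as written makes the post-dosing repeat the Week 12 CRP, whatever its date, and no other provision clearly prevents it. A valid value is displaced only when the visit fell on Day 83 or 84 and the repeat fell nearer Day 85.

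The consequence is confined to descriptive Week 12 outputs: CRP plots, JADAS27, ACR response and, on the default reading, inactive disease. A reader might infer that the trial's main conclusion is at risk. It is not, because the primary endpoint is at Week 2 and the key secondary endpoints are at Week 1.

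The shifts of 12.5 and 25 points are worst cases for one patient under an assumed 8:4 split, not expected effects. The frequency is unknown, and the 0 to 10% range is an assumption. The change is still worth making, because it is cheap and the label would otherwise misdescribe what was measured.

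**What to change.** Add to SAP 8.1: for efficacy variables, laboratory values from unscheduled visits later than the day after the last IMP dose are not assigned to Week 12 and are used only in safety summaries and listings. Values from the scheduled Week 12 visit and the Study Drug Discontinuation visit remain eligible under the existing rules.

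The restriction should go no wider. A cutoff on all efficacy variables could discard a scheduled Week 12 visit held two days after the last dose. It could also discard a discontinuation visit after Day 72 held two or more days after stopping, which would remove treatment failures from observed-data summaries.

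The cost is one sentence before database lock, and an occasional Week 12 CRP-based result becomes missing. SAP 8 uses all patients in the group as the default denominator, so a patient with missing inactive-disease status would by default count as not having inactive disease. That would produce the same 12.5- or 25-point distortion by another route. The table should therefore show such patients in a separate missing category.

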### 8.2 Handling of missing data and outliers

#### 8.2.1 Imputation for efficacy endpoints

For all endpoints related to the primary objective the following imputation will be used:

- Patients that discontinue study drug prior to Week 2 will be set to non-responders.
- For patients with missing information in any of the ACR30 components, that specific component will be set to no change. For patients with missing information on fever, the patients will be treated as having a presence of fever.

For the key secondary endpoints the following imputation will be used:

- Patients who have missing information on fever during 24 hours preceding Week 1 will be treated as having a presence of fever in the analysis.
- For the other secondary endpoints no imputation will be performed, i.e., all presentations will be based on observed data.

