8.3.5 Analysis related to key secondary objective

To evaluate the key secondary objective, the following endpoints will be analyzed:

- Absence of fever during the 24 hours preceding Week 1.

- Change from baseline in physician global assessment of disease activity (VAS) at Week 1.
- Change from baseline in patient/parent global assessment of overall well-being (VAS) at Week 1.
- Change from baseline in CRP at Week 1.

The absence of fever at Week 1 will be analyzed using a logistic regression model with treatment, age at onset of disease (< 16 years, ≥ 16 years) and glucocorticoid use (yes, no) as explanatory variables. Patients who discontinued study drug prior to Week 1 will be treated as having a presence of fever in the analysis. The estimated probability of absence of fever in each treatment group, the estimated odds ratio of anakinra to placebo, the corresponding 95 % confidence interval and the p-value from the model will be presented.

The three continuous endpoints; change in CRP, change in physician's global assessment of disease activity and change in patient/parent global assessment of overall well-being, will be analyzed using a mixed model repeated measurement with the measurements on the individual timepoints (i.e. Baseline and Week 1 or if the Week 1 visit is not performed due to Study drug discontinuation before Week 1 the Study drug Discontinuation visit will be used) as responses and with treatment, age at onset of disease (< 16 years, ≥ 16 years) and glucocorticoid use (yes, no), visit and treatment-visit interaction as fixed effects. For the comparison between anakinra (combined dose groups) and placebo for each endpoint, the estimated difference, the associated 95 % confidence interval and the p-value from the model will be presented.

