### 3.3.2 Secondary endpoints supporting the primary objective

The secondary endpoints supporting the primary objective are:

- ACR30 response at Week 1 with absence of fever attributable to the disease during 24 hours preceding Week 1.
- ACR50, ACR70 and ACR90 response at Week 1 and Week 2 with absence of fever attributable to the disease during 24 hours before Week 1 and 7 days preceding Week 2.
- Response in the **individual components** of ACR at Week 1 and Week 2. Response is defined as an improvement of > 30%, 50%, 70% and 90% from baseline.
  - o Physician global assessment of disease activity (VAS)

- o Patient/parent global assessment of overall well-being (VAS)
- o Number of joints with active arthritis
- o Number of joints with limitation of motion
- Assessment of physical function (CHAQ/SHAQ)
- o CRP (mg/L)
- Absence of fever during the 7 days preceding Week 2.

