### 12.2 Secondary endpoints supporting the primary objective

For ACR30, ACR50, ACR70 and ACR90, with absence of fever in the preceding 24 hours at Week 1 and ACR50, ACR70 and ACR90, with absence of fever in the preceding 7 days, at Week 2, the proportion of patients with a response in each treatment group, along with 95 % exact confidence intervals and exact tests of the difference in response between treatment groups, will be presented. The same exact methods as for the primary endpoint will be used. Patients who have discontinued study drug prior to the relevant week of the analysis (Week 1 or Week 2) will be treated as non-responders in the analyses.

The response in the individual components of ACR30, ACR50, ACR70 and ACR90, respectively, at Week 1 and Week 2 will be analyzed in the same way as the primary endpoint using exact statistical methods. The proportion of patients with a response in each group, and exact confidence intervals of the difference will be presented. Patients who have discontinued study drug prior to Week 1 will be treated as non-responders in the analyses of the individual components of ACR at Week 1 and patients who have discontinued study drug prior to Week 2 will be treated as non-responders in the analyses of the individual components of ACR at Week 2.

The numbers of patients with response/no response in the individual components of ACR at Week 1 and Week 2 will also be presented in bar charts.

The absence of fever at Week 2 will be analyzed in the same way as the primary endpoint using exact statistical methods. Patients who have discontinued study drug prior to Week 2 will be treated as having a presence of fever in the analysis.

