### 12.3 Key secondary efficacy endpoints

The absence of fever at Week 1 will be analyzed in the same way as the primary endpoint using exact statistical methods.

For each of the three continuous endpoints; change at Week 1 in CRP, in physician's global assessment of disease activity and in patient/parent global assessment of overall well-being, descriptive statistics for each treatment group will be calculated. For the comparison between anakinra and placebo, exact rank tests based on Wilcoxon scores will be used. The exact 95% confidence intervals based on the Wilcoxon rank statistic for the Hodges-Lehmann estimate of the treatment difference, will be calculated.

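### SAP 8.2.1 and SAP 12.2 set different cut-offs for early stopping in the Week 1 ACR analyses, and SAP 12.3 omits the protocol's early-stop rule for Week 1 fever

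*SAP*

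**What the plan says.** **Week 1 ACR endpoints.** SAP 8.2.1 opens its first block of rules with "For all endpoints related to the primary objective the following imputation will be used", and the first rule in that block is "Patients that discontinue study drug prior to Week 2 will be set to non-responders". It has one cut-off and makes no distinction by week of analysis. SAP 3.3.2 lists among the endpoints supporting the primary objective "ACR30 response at Week 1 with absence of fever attributable to the disease during 24 hours preceding Week 1", along with the higher ACR thresholds and the individual components at Week 1.

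SAP 12.2 describes how those endpoints are analysed and uses another cut-off. For the composite responses it says "Patients who have discontinued study drug prior to the relevant week of the analysis (Week 1 or Week 2) will be treated as non-responders". For the Week 1 components it says "Patients who have discontinued study drug prior to Week 1 will be treated as non-responders in the analyses of the individual components of ACR".

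In the protocol, section 8.4.1 attaches the before-Week-2 cut-off to the primary endpoint only. Section 8.3.4 uses a stop before Week 1 for the Week 1 components. For composite ACR it counts patients who have discontinued as non-responders but gives no time point.

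**Week 1 fever.** Protocol 8.3.5 states "Patients who discontinued study drug prior to Week 1 will be treated as having a presence of fever in the analysis", and the synopsis has the same rule. SAP 12.3 says only "The absence of fever at Week 1 will be analyzed in the same way as the primary endpoint using exact statistical methods". SAP 8.2.1 adds that missing 24-hour fever information at Week 1 is counted as fever.

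**The concern.** Two sections of the SAP give a programmer different instructions for the same patients, and neither is said to take precedence. A patient assessed on drug at Week 1 who stops a few days later has a genuine Week 1 result. One section keeps it and the other replaces it with non-response because of something that happened afterwards.

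For Week 1 fever the difficulty is an omission. Without the protocol's sentence, a patient who stopped before Week 1 is counted as febrile only if the fever information is missing. Protocol 6.5.1.9 has 24-hour fever recorded at a discontinuation visit held before Week 1, so such a patient may have a record.

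With the trial stopped early and at least 12 patients expected (SAP 4.2), one patient coded differently can change a nominal result. If the rule is still open once the blind is broken, the choice could be made knowing which result it gives.

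**Working it through.** The plan gives no figure on this point. Its planned size of 81 does not depend on these rules. For the record, that figure is reproduced by the continuity-corrected two-proportion formula (65% v 25%, 2:1, two-sided 5%, 90% power), which gives 27 placebo and 54 anakinra patients.

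**Step 1: the rules side by side.**

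| Patient | SAP 8.2.1 | SAP 12.2 / 12.3 | Protocol |
|---|---|---|---|
| On drug at Week 1, stops before Week 2; Week 1 ACR component | non-responder | observed result kept (12.2) | observed result kept (8.3.4) |
| Same patient; Week 1 composite ACR | non-responder | observed result kept (12.2) | no time point given (8.3.4) |
| Stops before Week 1, no fever record | fever (missing-data rule) | no rule for stopping (12.3) | fever (8.3.5) |
| Stops before Week 1, afebrile record from the discontinuation visit | not covered by the missing-data rule | no rule for stopping (12.3) | fever (8.3.5) |

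The first two rows are a direct conflict within the SAP. The last row is the gap for fever.

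**Step 2: can the last row occur?** SAP 8.1 maps Days 2 to 11 to Week 1 and lets unscheduled assessments contribute. A discontinuation visit before Week 1 falls in that window. Against this, the windows apply only where nothing else is specified, and SAP 8.5.2 says that separate eCRF forms ask about fever before Week 1 and before Week 2. It does not say whether the discontinuation-visit record may stand in for the Week 1 form. The case is possible, and the text does not settle it.

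**Step 3: what one patient does.** Assumptions: 12 patients split 8 anakinra to 4 placebo (the SAP's minimum at 2:1), one affected patient, two-sided Fisher exact test as in SAP 12.1. The documents give no number of early stops, so the range starts at no affected patient and no effect. One patient is 1/4 = 25 percentage points on placebo and 1/8 = 12.5 points on anakinra.

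The two-sided p-value is the sum of the hypergeometric probabilities of all tables no more likely than the one observed.

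- 8/8 v 2/4: both failures on placebo, C(4,2)/C(12,2) = 6/66 = 0.091.
- 8/8 v 1/4: all three failures on placebo, C(4,3)/C(12,3) = 4/220 = 0.018.
- 7/8 v 0/4: C(8,1)·C(4,4)/C(12,5) = 8/792 = 0.010.
- 6/8 v 0/4: C(8,2)·C(4,4)/C(12,6) = 28/924. The opposite extreme has the same probability, so p = 56/924 = 0.061.

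| Arm of the affected patient | Result counted as observed | Result set to failure |
|---|---|---|
| Placebo | 8/8 v 2/4, p = 0.091 | 8/8 v 1/4, p = 0.018 |
| Anakinra | 7/8 v 0/4, p = 0.010 | 6/8 v 0/4, p = 0.061 |

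For Week 1 ACR, the middle column is SAP 12.2 and the right-hand column is SAP 8.2.1. For Week 1 fever, the middle column uses the discontinuation-visit record and the right-hand column is the protocol's rule.

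**Step 4: how many patients might be overwritten.** Purely as an assumption, let 40% of placebo and 10% of anakinra patients stop between Weeks 1 and 2, with 25% of them Week 1 responders. The expected numbers are 4 × 0.40 × 0.25 = 0.4 placebo and 8 × 0.10 × 0.25 = 0.2 anakinra patients, under one in total.

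**The case against.** The best reply is that the specific section governs the general one. SAP 12.2 is the analysis section for these endpoints and gives the Week 1 cut-off twice, so the defect is one loosely scoped lead-in line in 8.2.1. This is the sensible reading and probably the intended one. But the SAP does not say so, and SAP 12.1 sends the reader to 8.2.1 for imputation. Nor does the reply help with fever, because 12.3 has no rule for early stopping to prefer.

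On fever, a reader might infer that no reading of the SAP agrees with the protocol. The documents do not support that. If only the Week 1 form in SAP 8.5.2 counts, a patient who stopped earlier and had no Week 1 visit has missing fever information and is set to febrile, which is the protocol's result. The protocol asks such patients for a discontinuation visit and a Week 2 visit, and 8.3.5 foresees that the Week 1 visit may not take place. What remains is that this reading is available but not stated. Another reading, in which analysing fever in the same way as the primary endpoint brings in the before-Week-2 cut-off, is not excluded either.

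The consequences are also limited. Key secondary endpoints are tested only if the primary succeeds, and SAP 8.4 calls secondary testing exploratory. SAP 12.1.1 includes a Week 1 ACR30 sensitivity analysis with actual data from patients who stopped, except for progressive disease, and SAP 12.1 lists ACR and component responses by visit. All of this stands. It limits the effect but does not fix the main rule, and the sensitivity analysis does not cover fever, the higher ACR thresholds or the components.

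**Conclusion.** The inconsistency is real and should be corrected; its reach is modest. SAP 8.2.1 and 12.2 conflict on all Week 1 ACR endpoints. SAP 12.3 leaves open how to count a patient who stopped before Week 1 and has an afebrile discontinuation-visit record.

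Three stronger inferences are not supported:

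- **That the SAP contradicts the protocol on every Week 1 ACR endpoint.** The conflict with the protocol is explicit for the components and for the scope of the before-Week-2 rule. For composite ACR the protocol gives no time point, so the firm conflict there is 8.2.1 against 12.2.
- **That overwriting Week 1 ACR touches the early-onset claim.** Early onset is the key secondary objective, with fever, the two global assessments and CRP as its endpoints. Week 1 ACR supports the primary objective. Of the four early-onset endpoints, only fever is affected.
- **That the error favours one arm.** The documents do not say in which arm early stops will fall, and the effect reverses with the arm.

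The p-values rest on the assumed 8:4 split and a single affected patient. They show that the rule could decide a nominal Week 1 result, not that it will.

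**What to change.** Make two changes before the SAP is locked and the blind is broken.

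1. In SAP 8.2.1, replace the fixed before-Week-2 cut-off by the one already in SAP 12.2: patients who "discontinued study drug prior to the relevant week of the analysis (Week 1 or Week 2) will be treated as non-responders". The primary endpoint keeps its Week 2 cut-off, because Week 2 is its relevant week.
2. In SAP 12.3, restore the protocol 8.3.5 sentence: "Patients who discontinued study drug prior to Week 1 will be treated as having a presence of fever in the analysis". This also removes the question whether the discontinuation-visit record counts for these patients.

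It would help to add whether a patient who stops at the Week 1 visit itself, where the discontinuation visit replaces the scheduled one, counts as having stopped before Week 1.

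The cost is two sentences of SAP text, three with the addition. No data collection, sample size or primary analysis changes.
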